## Researching the Effects of Airway Clearance Therapies in Cystic Fibrosis (REACT-CF)

### 1. Specific Aims

Mucus clearance is one of the primary innate defense mechanisms of the lungs, and impaired mucus clearance is believed to drive the development and progression of cystic fibrosis lung disease through a cycle of bacterial colonization, infection, inflammation, and mucostasis. Airway Clearance Therapies (ACTs) are a cornerstone of treatment in Cystic Fibrosis (CF), and are typically accomplished using one of a number of mechanical devices that are designed to facilitate mobilization of mucus from the airways. Despite the emphasis clinicians place on these therapies and the time patient spend performing them, little research is available to validate the efficacy of any specific device or technique; even less research exists on the comparative effectiveness of competing devices.

The biology underlying the transduction of physical forces applied with ACTs into effective mucus clearance has also been inadequately studied. Mechanical forces are known to stimulate release of signaling molecules (i.e. adenosine nucleotides and nitric oxide [NO]) from airway epithelia. These molecules are involved in the regulation of physiologic processes (i.e. ion transport, cilia beat frequency, and mucus secretion) that determine rates of mucociliary clearance (MCC). Until now, no studies have directly explored the linkage between these signaling molecules and *in vivo* rates of MCC. If in fact a significant relationship is discovered, the measurement of these molecules could provide simple, non-invasive biomarkers that reflect MCC rates and allow assessment of treatment effects from ACT and potentially other therapeutics.

In this study, we propose to objectively characterize the effect of ACTs that utilize different approaches by: 1) measuring MCC using gamma scintigraphy; and 2) exploring biologically plausible biomarkers that could help our understanding of the physiologic responses to ACT that facilitate mucus clearance. We also explore the effects and utility of a novel vibrating plate device as an ACT. Finally, the results of this study will be used to inform the design of future trials of effectiveness of ACTs.

Within this study, we will test several hypotheses:

**Hypothesis 1:** *Device-assisted airway clearance therapy using OPEP, HFCWO-vest, and whole-body vibration causes a demonstrable increase in MCC and expectorated sputum volume when compared to cough alone.*

**Hypothesis 2:** *Airway signaling molecules, including NO and purine nucleotides (e.g. ATP, adenosine), are associated with the regulation of MCC and mediate the increase in mucus clearance that occurs following the application of mechanical stimuli from OPEP, HFCWO-vest, and whole-body vibration.*

We will test these hypotheses through these specific aims:

**Specific Aim 1:** Measure the effects of 4 different ACT modalities on MCC, using gamma scintigraphy.

**Specific Aim 2:** Measure the effects of different ACT modalities on proposed regulators of MCC, including nucleotide levels (via exhaled breath condensate collection) and exhaled NO.

**Specific Aim 3:** Examine associations between biomarkers of airway mechanical stimulation and measured MCC.

**Specific Aim 4:** Determine what study characteristics would be needed to more fully assess the effectiveness of ACTs, including sample size, study design features, and outcome measures.

## 2. Background And Rationale

### *CF and MCC*

CF lung disease results from abnormal ion transport, dysfunctional regulation of airway surface liquid (ASL), and reduced mucus clearance. Recent work has led to the development of a 2-gel model of the ASL layer where dehydration and increased osmotic pressure in the overlying secreted gel can result in volume depletion of the periciliary gel layer. This in turn may lead to adhesion of mucus plaques to airway epithelial surfaces and disruption of ciliary motion and cough-stimulated mucus clearance. In CF subjects, we have shown that cilia and cough driven mucus clearance is abnormal, and that additional reduction in MCC contributes to the onset of a pulmonary exacerbation. Not surprisingly, effective airway clearance of mucus is a cornerstone of therapy and of great importance in preventing disease exacerbations and progression of airways disease.

### *Airway Clearance Therapies*

Airway clearance has been, and continues to be, a central part of CF care. Techniques of manual chest percussion and postural drainage have largely been supplanted in adolescents and adults by the use of ACT devices, which afford patients independence. These devices, together with voluntary breathing techniques (active cycle of breathing, autogenic drainage, huff coughing) and exercise, enable individuals with CF to better expectorate tenacious airway secretions. Currently available ACT devices include pneumatic high frequency chest wall oscillatory devices, typically worn as a vest (The Vest®, AffloVest®, inCourage®, SmartVest®), a variety of oscillatory and non-oscillatory positive expiratory pressure (PEP) devices (Flutter®, Acapella®, Aerobika®, RC-Cornet®, TheraPEP®, Hydrapep®), and acoustical percussors (Vibralung). FDA clearance of these devices do not require proof of efficacy and, according to an expert review of available literature, there is insufficient evidence to assess the long-term effects of ACTs as well as inadequate evidence to support the superiority of one ACT over another. Therefore, prescription of such devices is often determined by the subjective preference of each patient, based on what “feels” most effective to them, and/or provider habits and/or biases with little objective data guiding decisions.

### *Whole Body Vibration In Exercise And Therapy*

The use of whole body vibration (WBV) via a vibrating plate was developed for use in personal fitness and recreation and not as a medical therapy or intervention. These devices consist of a large plate that vibrates at frequencies generally between 20 and 70hz and with a displacement of 1-5mm. The effect of these devices is to constantly accelerate and decelerate the whole body in an oscillating manner. This acceleration is described by the simple harmonic motion equation and is proportional to the displacement of the plate and to the square of the frequency of vibration. These variables are the settings on the device. Studies of WBV in bone density and musculoskeletal outcomes in older adults did not show benefit for acceleration  $<1\ g$ , but other studies did show some benefit for WBV exerting higher magnitudes (1 to 8  $g$ ). A pilot study of WBV in individuals with cystic fibrosis showed an improvement in muscle strength and performance. These devices have not been studied as a means of airway clearance therapy, but there is anecdotal support for their use for airway clearance by individuals with CF. Furthermore, studying their effect as an ACT allows us to test the hypothesis that high energy devices, even those not specifically engineered for airway clearance such as WBV platforms, may be as effective in ACT as those devices that were specifically engineered to affect the respiratory system.

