#### **4. Rationale for proposed study**

We intend to carry out this pilot study to determine the effect size (and variability) of cough alone and various ACT devices on MCC, signaling molecules, and sputum volume. We will also explore the correlation between MCC and signaling molecules, and compare a novel exercise device using whole body vibration to traditional ACT methods.

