## Data analysis:

[name], biostatistician for the UNC CF Center, has been closely involved in the study design and will be responsible for overseeing the database creation and management, as well as performing final statistical computations during data analysis.

**Primary comparison:** MCC will be visualized using a whole right lung clearance vs. time plot from immediately after isotope inhalation through 274 minutes post-inhalation. The area under this curve (AUC-Clr274), will be used to reflect “total clearance”, and will serve as the primary outcome of this study. We will compare AUC-Clr274 in huff-cough alone to AUC-Clr274 measured with each of the ACT modalities (HFCWO-vest, OPEP device, and WBV device).

**Secondary comparisons:** AUC-Clr over other intervals (i.e. 94 min and 180 min), and from other lung regions of interest (i.e. peripheral and central lung zones) will be calculated and compared in similar fashion as above. Furthermore, the change in the rate of clearance (represented by the slope of the MCC curve,  $d\text{Clr}/dt$ ) before (0-16 minutes of MCC curve;  $d\text{Clr}/dt_{0-16}$ ) versus during/after the initial ACT intervention (16 – 56 minutes;  $d\text{Clr}/dt_{16-56}$ ) will be used to compare the immediate effects of each ACT versus. huff coughs alone. The mean changes in EBC purines concentrations and FeNO, (before vs. after ACT) will be calculated. If these are found to be different from zero, a comparison between huff-cough alone and each of the ACT modalities will be made. Total sputum weights and % solids at baseline and after each ACT 40 minute period will be compared across each of the ACT modalities. We will also assess for a relationship between changes in EBC measurements, FeNO, and changes in MCC.

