Means, standard deviations and 95% confidence intervals will be calculated for MCC parameters and all secondary outcome measures. A repeated measures model will be used to compare the primary and secondary outcome measures, with the subjects considered as random factors. For hypothesis one and three, MCC values from huff-cough alone will be compared to traditional ACT methods (HFCWO-vest and OPEP) and Whole Body Vibration to test the null hypothesis that there is no difference in MCC between huff-cough and a) HFCWO-vest; b) OPEP; and c) WBV. For hypothesis two, biomarker values pre and post each ACT intervention will be compared using paired t-tests to test the null hypothesis [i.e. there is no difference between candidate biomarker concentration before and after use of a) HFCWO-vest, b) OPEP, and c) WBV]. We will also compare the change in biomarker values across different methods using a repeated measure model. Finally, we will explore the strength of the relationship between MCC responses and the corresponding change in candidate biomarker values by calculating the Spearman’s Correlation Coefficient.

Breath sounds data will be collected as a pilot project, and will not be subject to statistical measures.

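### The plan asks how whole-body vibration compares with purpose-built airway clearance devices, but every mucociliary clearance analysis compares each modality only with huff-cough

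*Combined protocol and SAP*

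**What the plan says.** Two places set up a comparison of WBV with the established devices. The Background subsection on whole-body vibration says that studying WBV permits a test of the hypothesis that high-energy devices not designed for airway clearance "may be as effective in ACT as those devices that were specifically engineered to affect the respiratory system". Section 4 (Rationale) says the study will "compare a novel exercise device using whole body vibration to traditional ACT methods".

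The Data analysis section specifies these MCC analyses:

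- **Primary:** AUC-Clr274 under huff-cough alone is compared with AUC-Clr274 measured "with each of the ACT modalities (HFCWO-vest, OPEP device, and WBV device").
- **Secondary AUCs** (other intervals and lung regions): compared in the same way as the primary.
- **Slope change** before versus during the first intervention: it "will be used to compare the immediate effects of each ACT versus. huff coughs alone".
- **Null hypotheses:** "there is no difference in MCC between huff-cough and a) HFCWO-vest; b) OPEP; and c) WBV".

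Comparisons across modalities are planned for other outcomes. Sputum weight and percent solids are compared across the ACT modalities, and for biomarkers the plan says "We will also compare the change in biomarker values across different methods using a repeated measure model". No such comparison is specified for MCC, and no margin or rule for concluding equal effectiveness appears anywhere.

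The numbering is also loose. The analysis text begins "For hypothesis one and three, MCC values from huff-cough alone will be compared to traditional ACT methods", but the Specific Aims list only two hypotheses. Hypothesis 1 there concerns an increase over cough alone.

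**The concern.** A question about WBV relative to vest and OPEP needs an estimate of WBV minus vest and of WBV minus OPEP. The planned MCC analyses give neither. Rejecting the null of no difference between WBV and huff-cough shows that WBV does something. Failing to reject it says nothing about the other devices. Three separate comparisons with a shared control do not add up to a comparison among the three.

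A WBV-versus-device significance test would not be enough by itself either. With about 10 subjects, a non-significant difference is weak evidence of similarity.

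The stake is how WBV is described when the pilot is reported. Section 3 says the results may inform the design of later ACT trials. Without a planned interval for WBV minus each device, the question raised in the Background and Rationale would be answered informally from the huff-cough results.

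**Working it through.** **1. Question against analysis**

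| Stated intent | MCC analysis specified |
|---|---|
| WBV versus engineered devices (Background) | None |
| WBV versus traditional ACT methods (Rationale) | None |
| Each device versus cough alone (Hypothesis 1) | AUC-Clr274, other AUCs, slope change, three nulls |

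The gap concerns the first two rows. Hypothesis 1 is matched by its analysis.

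**2. Inputs** (Sample size estimate and Missing Data sections)

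Planned effect over huff-cough 20.0; SD of the paired difference 15.1; two-sided alpha 0.05; 10 subjects; 7 stated as sufficient for 80% power.

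**3. The plan's own figure**

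d_z = 20.0/15.1 = 1.325 (plan: 1.33). Exact noncentral-t power for a paired two-sided test is 73.7% at n = 6 and 83.0% at n = 7. The stated 7 is reproduced. It covers a change from huff-cough only.

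**4. Precision of WBV minus one device at n = 10**

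Assumption: 15.1 also applies to device-versus-device differences. The documents give no such SD; 15.1 comes from hypertonic saline versus baseline.

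Half-width = t(0.975, df) × SD/√n, with 15.1/√10 = 4.775.

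- Paired, df = 9: 2.262 × 4.775 = 10.8.
- Pooled repeated-measures error over four visits, df = 3 × 9 = 27: 2.052 × 4.775 = 9.8. The simulated average is 9.7.

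Relative to the planned effect: 9.7/20 = 0.49 and 10.8/20 = 0.54. For other SDs the same formula gives 6.5 (pooled) to 7.2 (paired) at SD 10, and 13.0 to 14.3 at SD 20.

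**5. What a formal claim would face**

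Take an illustrative margin of 10, half the planned effect, and require the lower 95% bound of WBV minus device to exceed −10. Simulation: pooled model, four visits, SD 15.1 for every pairwise difference, n = 10.

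- WBV truly equal: passes against one device in about 52% of trials and against both in about 36%.
- WBV effect truly 10: passes against one device in 2.5%.
- SD sensitivity for a truly equal WBV against one device: 86% at SD 10, 33% at SD 20.

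By paired t-test, 80% power for a truly equal WBV at this margin needs 20 subjects; n = 10 gives 46%.

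**6. Why the planned tests cannot stand in for the contrast**

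Suppose WBV's true effect is 10 and that of vest and OPEP is 20 (hypothetical). With the pooled model at n = 10:

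- Vest and WBV are both significant against huff-cough in 52% of trials (86% at SD 10, 32% at SD 20).
- A WBV-versus-vest test, which the plan does not specify for MCC, is non-significant in 48% (54% by paired t-test; pooled 14% at SD 10, 67% at SD 20).

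Neither pattern separates a half-effective WBV from an equal one.

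**The case against.** The strongest case against the point is that this is a pilot meant to measure effect sizes and variability. The equal-effectiveness sentence is motivation, worded as a possibility, and sits in the Background. The two listed hypotheses claim no equivalence, and the nulls fit Hypothesis 1. The unexplained third hypothesis may simply have been WBV versus huff-cough, which would leave only a numbering slip. The plan also promises 95% CIs for MCC parameters and a model from which any contrast can be drawn.

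Much of this stands. The primary comparison is unaffected, nothing can safely be built on the third hypothesis, and demanding a margin from a 10-subject pilot is a debatable choice. It does not remove the gap. The Rationale repeats the comparative aim outside the Background, and the promised intervals are not specified for WBV minus a device.

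A reader might infer something stronger: that the plan would let a half-effective WBV pass as equally effective about half the time. The documents do not support that. They contain no rule that reads joint significance, or non-significance, as equal effectiveness. The 52% in step 6 is essentially the power to detect a true WBV effect of 10 over huff-cough, which is a correct rejection. The 48% to 54% belongs to a test that is not in the plan. The figure also moves with the rule imagined. By paired tests it is 36% for non-significance against both devices, 30% for significance against huff-cough plus non-significance against one device, and 22% for the same against both.

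**Conclusion.** The point holds as a mismatch between a stated question and the specified analysis. The MCC analyses can show whether WBV differs from huff-cough; they cannot show how it compares with vest or OPEP. This rests on the text alone and needs no numerical assumption.

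The size of the issue is one of precision. If SD 15.1 carries over to device-versus-device differences, 10 subjects give an interval of roughly ±10 around WBV minus a device, half the planned effect. That is informative for planning a later trial but leaves little ability to establish equal effect. The margin of 10 and the half-size WBV effect are illustrations, not figures from the plan. The point does not establish an error rate for the plan, and it leaves the huff-cough comparisons intact. It is worth correcting before analysis because it changes what the trial can conclude about WBV.

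**What to change.** In the Data analysis section:

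1. Add WBV minus vest and WBV minus OPEP on AUC-Clr274, each with a two-sided 95% CI from the planned repeated-measures model, and name them as the analysis for the Background and Rationale question. The three device visits are already in randomised order, so the design supports these contrasts.
2. State that neither significance of WBV against huff-cough nor a non-significant WBV-versus-device difference will be read as showing that WBV is as effective.
3. Reword the Background sentence so that the study will *estimate how WBV compares with* the engineered devices, and correct the reference to a third hypothesis.

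A pre-set margin on the AUC-Clr274 scale is needed only if the sponsor keeps a formal equal-effectiveness claim. The chances of success in step 5 should then be stated, including about 36% when both devices must be cleared.

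The cost is two extra intervals from data already collected and a more modest claim about WBV. No extra subjects, visits or procedures are needed.

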### *Biomarkers of Mucus Clearance*

Gamma scintigraphy has been developed as an important tool in the measurement of MCC, utilizing a technique of inhalation of an aerosolized radiotracer followed by particle detection and image processing. A standard operating procedure was developed at UNC to report resting MCC as well as cough clearance and has been used in several single and multisite studies. Pharmacologic therapies in CF such as hypertonic saline and ivacaftor (in patients with the G551D-mutation) have yielded demonstrable improvement in clinical outcomes and MCC, whereas reduced MCC was observed at the start of a pulmonary exacerbation. Conversely, no improvement in MCC was observed with agents that have also failed to yield meaningful clinical improvements in CF (e.g. amiloride, UTP, denufosal). Together, these observations suggest that the MCC technique may have the ability to predict the clinical effectiveness of a subgroup of CF therapies.

[figure not shown]
Given the importance of MCC as an innate lung defense, it is not surprising that there are overlapping systems of local regulators that control the physiologic processes that dictate MCC rates, including ion transport and ciliary beat frequency (CBF). Extracellular adenosine 5'-triphosphate (ATP) is the endogenous ligand for P2Y2 receptors, which in turn stimulates calcium activated chloride channels, inhibits the epithelial sodium channel (ENaC), and increases CBF. ATP release in airway epithelia is very sensitive to mechanical stimulation, and could provide a mechanistic link between ACT or exercise and mucus clearance. Adenine nucleotide levels have been successfully measured in exhaled breath condensate (EBC) specimens from CF patients, and likely reflect airway inflammation as well.

Another airway mediator that is linked to MCC is NO. NO, via cGMP, is known to increase CBF and may inhibit ENaC activity via the same signaling pathway. Exhaled NO levels are significantly reduced in diseases characterized by reduced MCC (PCD and CF), and increase in response to ivacaftor in G551D-CF patients. NO production may also be increased by shear stress, at least in endothelial cells. Once again, like ATP, NO levels in the airway may be modulated by ACTs and impact MCC.

[figure not shown]
### *Slow Inhalation, Large Particle MCC Method Development*

A multicenter MCC SOP was developed and tested by the UNC group and has been employed in several CFF and industry funded studies (GOAL, VX661-111, AlgiPharma, PROSPECT). This method, which utilizes a relatively fast and shallow breathing pattern during isotope inhalation, emphasizes clearance from the large airways, but is less able to characterize small airway clearance. We, therefore, used funding from the MCC Consortium (CFF) to develop and test alternative methods for assessing particle clearance from the small airways. In this work, we used concepts introduced by Lindstrom et al., where the very slow inhalation of large aerosol particles (SILP) can be used to better target small airways. Slow inhalation (80 ml/sec) of 5  $\mu$ m and 9  $\mu$ m MMAD particles was compared to our standard SOP (5  $\mu$ m MMAD with inhalation rate of 500 ml/sec) in healthy, CF and COPD subjects. First, while large airway clearance appeared unchanged (definition: whole lung clearance in first 90 minutes), the fraction of isotope that cleared between 90 minutes and 6 hours more than doubled, signifying greater small airway deposition via avoidance of alveolar deposition (Figure 1A). Second, we observed an improved ability to distinguish pathological clearance patterns in diseased subjects (Figure 1B), in contrast to our prior observation that only peripheral clearance and cough clearance appears to be impaired in CF subjects with our standard measurement protocol. Finally, we tested the relative responsiveness of the SILP method using hypertonic saline (HS), given 100 minutes, 4.5 hours, and 16 hours after isotope inhalation, to simulate a highly active and durable MCC stimulant. In these experiments, a surprisingly large acute effect of HS was observed (Figure 2A), particularly with the 9  $\mu$ m particle,

and every subject was observed to be a “responder”, as opposed to prior observations that only ~60% of subjects acutely respond to HS when using the traditional MCC SOP (Figure 2B). In summary, this new methodology appears to have significant advantages to the traditional MCC measurement protocol typically used in multicenter studies.

**Figure 1:** A) Increased small airway clearance signal with slow inhalation of 9  $\mu\text{m}$  particles, vs. slow inhalation of 5  $\mu\text{m}$  particles or the standard MCC protocol, (shown with COV, coefficient of variation). B) SILP MCC method distinguishes CF from health and COPD clearance patterns.

**Figure 2:** A) Marked treatment effect of repeated doses of HS given after SILP isotope inhalation. B) Analysis of response to HS using absolute change in clearance from baseline. HS was given after slow inhalation of 5 $\mu\text{m}$  and 9 $\mu\text{m}$  particles (lower 2 panels), and is compared to the acute response to a single HS dose using the traditional MCC SOP (historical data; Donaldson et al. NEJM 2006).

